4.3 Data collection process

4.3.1 Outpatient data collection: The patient's first outpatient visit data and each outpatient follow-up visit data include main symptoms, blood β -HCG, ultrasound and infection-related indicators.

4.3.2 Data collection for inpatient surgery includes: preoperative symptoms; serum β -HCG, ultrasound and infection-related indicators; surgical data; and postoperative medication.

4.3.3 Follow-up after surgical treatment:

(1) If the ultrasound examination 3 days after the operation shows no pregnancy residue or the diameter of the residue is less than 0.5cm, follow up by phone or WeChat 1 month later to ensure that the patient's menstruation is over and to have a follow-up examination of β -HCG, ultrasound and other indicators at the outpatient clinic to determine whether the treatment has ended.

(2) If the ultrasound examination on the 3rd day after surgery shows that the

diameter of the retained pregnancy tissue is greater than 0.5cm, follow up by phone or WeChat half a month later to ensure that the patient goes to the outpatient clinic on schedule for β -HCG, ultrasound and infection indicators, and to determine the subsequent treatment plan.

4.3.4 Data collection after treatment: Menstrual flow, ultrasound findings of intrauterine adhesions, and endometrial thickness were collected during outpatient follow-up examinations three times after the end of treatment.

4.3.5 Data collection on reproductive outcomes: For patients who wish to have children, follow-up by telephone will continue every 3 months. If the patient has not become pregnant after 1 year of follow-up, the follow-up will be terminated. If the patient becomes pregnant within 1 year, follow-up will continue until the pregnancy is terminated, including whether there is spontaneous abortion, premature birth, full-term birth, stillbirth, or stillbirth.

5. Data Collection

5.1 General information: age, parity, number of previous intrauterine procedures, history of intrauterine adhesions, occupation, and education level.

5.2 Preoperative data on retained products of pregnancy: gestational age at termination; time of termination; serum β -HCG; imaging data (including ultrasound and MRI: uterine size, distance from the internal cervical os to the fundus, location of the retained products of pregnancy, maximum diameter, blood flow, presence of arteriovenous fistula (blood flow grade 1-6 in the retained products of pregnancy and surrounding uterine wall on color Doppler ultrasound), presence of placenta accreta, presence of intrauterine adhesions, uterine septum, uterine fibroids, adenomyosis. For the expectant management group, complete blood count, serum β -HCG, CRP, and ultrasound data from each follow-up examination should be collected.

5.3 Preoperative routine examination data : routine vaginal discharge test, HPV/TCT, complete blood count, liver and kidney function tests, electrolytes, coagulation function tests, thyroid function tests, serum β -HCG, anti-Müllerian hormone test, pre-transfusion examination, electrocardiogram, chest X-ray, 3D color Doppler ultrasound of the uterus and bilateral adnexa, and other relevant examinations. If a 3D ultrasound has been completed within one week in the outpatient clinic, it does not need to be repeated during hospitalization.

5.4 Surgical data: Date of surgery; depth of uterus; location and size of the gestational sac; operation time (from the start of the distension procedure to the withdrawal of the endoscope); amount of intraoperative blood loss; whether there is any retained gestational sac after surgery; clarity of the surgical field; volume of distension fluid in and out; whether there is a decrease in blood oxygen saturation;

whether complications such as uterine perforation, acute left heart failure, or gas embolism occur.

5.5 Postoperative follow-up data: serum β -HCG, complete blood count, CRP, procalcitonin (not required), ultrasound to check for retained products of conception, and if so, record the maximum diameter of the retained products.

5.6 Three months after treatment , outpatient follow-up data will be collected, including menstrual flow, ultrasound findings of intrauterine adhesions, endometrial condition, whether intrauterine adhesion surgery was performed, and intrauterine adhesion score.

5.7 Pregnancy outcome data collection: pregnancy rate after 1 year of trying to conceive ; miscarriage rate, premature birth rate, full-term birth rate, stillbirth rate, and stillbirth rate in subsequent pregnancies.

6. Efficacy evaluation

6.1 Main observation indicator: Incidence of intrauterine adhesions.

6.2 Secondary observation indicators: reoperation clearance rate; incidence of active bleeding and infection during expectant treatment in the expectant treatment group; pregnancy rate, live birth rate, and miscarriage rate one year after treatment.

7. Safety Assessment

7.1 Safety indicators: the expected probability of active bleeding and infection during treatment.

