IV. Research Design

1. Research Subjects

who were diagnosed with retained products of pregnancy by ultrasound at outpatient clinics of various research units between June 2022 and June 2024, and who met the inclusion criteria but did not meet the exclusion criteria, were all enrolled consecutively.

Inclusion criteria: age 18-45 years, clinical diagnosis of retained products of conception, and ultrasound showing a lesion with a maximum diameter ≥ 0.5 cm.

Exclusion criteria: 1) Active bleeding requiring immediate surgical intervention; 2) Significant infection; 3) Severe organ dysfunction, including coagulation disorders.

Note: Patients with cervical tissue impacted in the cervical canal who have undergone clamping treatment and do not meet the exclusion

criteria can be included in this study;

2. Grouping

Because there is currently no unified treatment plan for retained products of pregnancy in uterus, the timing of active surgical evacuation versus expectant management until the planned surgery remains controversial, and the optimal timing for surgical evacuation is not uniform. In clinical practice, physicians, based on fully informed consent, choose active surgical treatment or expectant management according to the patient's wishes, and perform surgery when necessary. This study does not interfere with patient treatment; it only designs and collects relevant data in advance. No additional examinations or tests are performed on patients during the study process, and all procedures are conducted according to standard clinical practice. After treatment, patients are divided into an active surgical group and an expectant management group based on their chosen treatment plan, and data are statistically analyzed.

3. Sample size and allocation

The sample size was determined based on the incidence of intrauterine adhesions, the primary outcome measure. According to previous research results, the intrauterine adhesion rate in the expected group was 5.38%, and the intrauterine adhesion rate in the patients undergoing active surgery was 14.29%. The Type I error was 0.05, the power was 90%, and the sample size was calculated using PASS to obtain a total of 460 cases. Based on a 20% follow-up dropout rate, the sample size was calculated to be 576 cases. It is expected that 600 cases will be included, with 120 cases from the lead institution and an average of 40 cases from the other 12 research institutions.

4. Research Process

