7.2 Reporting and follow-up of adverse events and serious adverse events

Possible adverse events: active bleeding; infection; the following are considered serious adverse events: massive bleeding requiring emergency interventional treatment; severe infection with systemic toxicity symptoms or pelvic abscess are considered serious adverse events.

Any adverse events or serious adverse events that occur during the research process must be reported to the responsible unit and other collaborating research units within 3 days, along with an analysis of the causes.

8. Statistical Analysis: SPSS 26.0 software was used to process the data .

Normally distributed measurement data were expressed as ($\bar{x} \pm s$), and t-tests were used for comparisons between two groups; analysis of variance was used for comparisons among multiple groups. Non-normally distributed measurement data were expressed as the median, and a nonparametric rank-sum test was used. Count data were expressed as χ^2 . The χ^2 test or Fisher's test was used. $P < 0.05$ was considered statistically significant.

9. Clinical Research Management

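### One-year pregnancy is collected by three-monthly calls, but section 8 offers only chi-square/Fisher, which cannot use partial follow-up; a life-table analysis would be a cheap improvement

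*Protocol*

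**What the plan says.** - **Follow-up (Protocol 4.3.5).** Women who wish to have children are telephoned at three-month intervals. "If the patient has not become pregnant after 1 year of follow-up, the follow-up will be terminated". Women who conceive within the year are followed to the end of the pregnancy.
- **Outcome (6.2).** The secondary indicators include "pregnancy rate, live birth rate, and miscarriage rate one year after treatment". Section 5.7 instead counts the pregnancy rate from a year of trying to conceive.
- **Analysis (8).** The methods named are the t-test, analysis of variance, a rank-sum test, and chi-square or Fisher's test for counts ("Count data were expressed as χ^2"). No time-to-event method is named.
- **Groups (IV.2).** Women are placed in the active-surgery or expectant group according to the treatment they chose.
- **Loss (IV.3).** "Based on a 20% follow-up dropout rate, the sample size was calculated to be 576 cases". This figure belongs to the sample size for intrauterine adhesions, the primary outcome. No loss rate is given for the pregnancy calls, overall or by group.

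**The concern.** Following women at regular calls until pregnancy or one year produces time-to-event data, some of it partial. A test on pregnant yes/no needs a final answer for each woman it includes. A woman reached at months 3 and 6, not pregnant, and then lost has no such answer, yet she contributed six months of information.

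Two simple ways of forcing an answer err in opposite directions. Counting her as not pregnant lowers the rate. Dropping her raises it if pregnancies reported before loss are kept, because a woman who conceives early is already counted and only women not yet pregnant can drop out of the denominator. If loss is equal in the two groups, the bias is the same in both. If it differs, the groups separate without any true difference, or a true one is masked. The groups are formed by choice, so equal loss is not guaranteed, and protecting fertility is part of the stated research objective.

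**Working it through.** **1. The plan's own figure.** Inputs from section IV.3: adhesion rates 5.38% and 14.29%, Type I error 0.05, power 90%. Taken as two-sided with 1:1 allocation and unpooled variance:

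n per group = (1.960 + 1.282)² × (0.0538×0.9462 + 0.1429×0.8571) / (0.1429 − 0.0538)² = 10.507 × 0.17339 / 0.007939 = 229.5, rounded up to 230, or 460 in total. Then 230/0.8 = 287.5, rounded up to 288, or 576 in total.

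Both stated figures reproduce. The sample size is not at fault, and it was not built for pregnancy.

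**2. Inputs for the pregnancy outcome.** The protocol gives no pregnancy rate, no loss by group and no number of women wishing to conceive. Assumed here: true 12-month rate F = 60% in both groups, constant hazards, loss unrelated to fertility, 150 women per group, and 12-month loss D of 10% v 30%.

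**3. Bias in the rate, pregnancies reported at once.** With λ = −ln(1−F) and μ = −ln(1−D):

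- reported pregnant = λ/(λ+μ) × [1 − (1−F)(1−D)]
- lost first = μ/(λ+μ) × [1 − (1−F)(1−D)]

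For D = 20%: λ = 0.916, μ = 0.223. Reported pregnant = 0.804 × 0.68 = 54.7%; lost = 0.196 × 0.68 = 13.3%. Dropping the lost gives 0.547/0.867 = 63.1%. The truth is 60%.

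| 12-month loss | Lost = not pregnant | Lost dropped, earlier pregnancies kept |
|---|---|---|
| 10% | 57.4% | 61.5% |
| 20% | 54.7% | 63.1% |
| 30% | 51.8% | 64.9% |

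**4. With pregnancies learned only at quarterly calls.** A pregnancy in the interval before a missed call is also unseen, so the gap for lost = not pregnant widens. Per quarter, conception q = 1 − 0.4^(1/4) = 0.2047; loss l = 1 − 0.9^(1/4) = 0.0260 or 1 − 0.7^(1/4) = 0.0853.

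Reported pregnant = (1−l)q × [1 − (1−F)(1−D)] / [1 − (1−l)(1−q)]:

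- 10% loss: 0.1994 × 0.64 / 0.2254 = 56.6%
- 30% loss: 0.1873 × 0.72 / 0.2726 = 49.5%

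Dropping the lost: 0.566/(0.566 + 0.36) = 61.1% and 0.495/(0.495 + 0.28) = 63.9%.

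**5. False-positive rate, 150 per group, no true difference.**

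- Lost = not pregnant: standard error √(0.530×0.470×2/150) = 0.0576; shift 0.0715/0.0576 = 1.24; rejection about 1 − Φ(1.96 − 1.24) = 24%.
- Lost dropped: about 139 and 116 women remain; standard error 0.061; shift 0.027/0.061 = 0.45; rejection about 7%, both tails.
- Simulation (8,000 trials, quarterly detection, censoring at the last completed call): **25.2%**, **7.7%**, and **5.1%** for the log-rank test.

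**6. Sensitivity.**

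- Loss 15% v 25%, otherwise as above: about 11% (lost = not pregnant) and 5.4% (dropped).
- True rate 30-70%, 150-300 per group, loss from 15/25% to 5/35%: 7-87% if lost = not pregnant, 5-16% if dropped.
- Equal loss of 20%: about 5% for every method.
- All lost women excluded, with loss unrelated to the final outcome: 5% even at 10/30% loss.

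**7. Power.** At an assumed 50% v 65%, with 20% loss in both groups and 150 women per group: chi-square 68.0% (lost = not pregnant) or 69.1% (dropped), life-table log-rank 73.1%. The gain is 4.0 to 5.1 points.

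**The case against.** The strongest reply is that a pregnancy rate at a fixed time is a proportion, and chi-square is valid for it when follow-up is complete. The harm arises only from the rule for lost women. The protocol states none, and such a rule is commonly left to a statistical analysis plan, which is not available here. This stands: the absence of the rule is not an error. What remains is that the methods section 8 does name cannot use the repeated calls that section 4.3.5 prescribes.

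A reader might infer that the plan will produce a false fertility difference. The documents do not support that, for four reasons.

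- The sentence on stopping at one year sets a planned end common to both groups. It does not describe loss.
- The 20% dropout was set for the adhesion sample size and is not split by group.
- The background remark that expectant management needs high compliance concerns the treatment period. The pregnancy calls follow the same telephone schedule in both groups. The 10% v 30% split is therefore an assumption.
- Excluding every lost woman is unbiased if loss is unrelated to outcome. That would, however, mean discarding pregnancies already reported by women who later fall out of contact, so it is not the natural data set.

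It is also fair to say that a life table does not cure self-selection. Confounding can give a false difference even with complete follow-up.

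**Conclusion.** The point holds as a worthwhile improvement to one secondary analysis, in the subset of women wishing to conceive. It is not an error in the plan. Chi-square/Fisher cannot use partial follow-up. Under either simple handling rule in the concern, unequal loss would inflate the false-positive rate: to about 25% or 8% at an assumed 60% true rate, 150 women per group and 10% v 30% loss, against about 5% for a log-rank test. None of those inputs comes from the protocol, and the figures move widely with them. With equal loss there is no inflation, and the benefit is about 4-5 points of power.

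The conflict over the time origin, trying to conceive in 5.7 against end of treatment in 6.2, can be read directly from the text. It has to be settled before any one-year analysis is fixed.

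**What to change.** 1. **Reconcile the time origin** in sections 5.7 and 6.2. End of treatment needs no new data. Start of trying to conceive would need a date that sections 5.1 to 5.7 do not list.
2. **Add to section 8:** pregnancy within one year will be analysed as time to pregnancy in three-month intervals, with women not known to be pregnant censored at their last completed call. The 12-month cumulative rate (life-table or Kaplan-Meier) will be given per group with a 95% CI. Groups will be compared by a log-rank test or a discrete-time (complementary log-log) model. The crude proportion will be a secondary display, with the number lost in each group and the rule used for them.

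**Cost:** a sentence or two and, with end of treatment as origin, no extra data.

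**Limits:** the method assumes that censoring is unrelated to fertility within each group. It does not address confounding from self-selected groups, and it does not cover live birth or miscarriage, which need their own definitions.

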In the diagnosis of RPOC, clinical practice usually combines the patient's history of delivery or miscarriage, symptoms of persistent or recurrent vaginal bleeding, serum β -HCG level, and transvaginal/abdominal Doppler ultrasound showing heterogeneous masses in the uterus to make a definitive diagnosis. The sensitivity of transvaginal Doppler ultrasound can reach 94%, and the specificity can reach 98% ^[2], so it is widely used in the diagnosis of retained products of pregnancy. As a supplementary means of ultrasound, pelvic MRI has more characteristic features and can clearly show the anatomical structure of the uterus, assess the relationship between the placenta and the myometrium, and clarify the location and depth of implantation, which is of great significance for the diagnosis and differentiation of RPOC ^[3].

The short-term complications of RPOC include vaginal bleeding and infection, while the long-term complications include intrauterine adhesions and infertility ^[4]. A study by Ben - Ami I proposed that retained products of conception are an independent risk factor for infertility ^[5].

In terms of the treatment of retained products of pregnancy, the main clinical treatment methods are divided into surgical treatment and non-surgical treatment. Non-

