surgical treatment mainly includes expectant management and drug treatment. A retrospective cohort study by Wada Yoshimitsu ^[6] included 54 patients with RPOC, of whom 44 patients chose expectant management. 34 patients (77%) had their retained pregnancy tissue expelled spontaneously without intervention and did not require surgical treatment. The other 10 patients (23%) underwent hysteroscopic surgery for "persistent vaginal bleeding" and concluded that expectant management is effective and can reduce the number of intrauterine operations. Zeng Wenjuan ^[7] et al. found that although the vaginal bleeding time was longer after expectant management than after curettage, no serious hemorrhage occurred. They also suggested that expectant management is equally safe and effective compared with curettage and can replace some curettage treatment. However, expectant management has a long follow-up time and requires high patient compliance. A meta-analysis by Li Mengxi ^[8] believed that expectant management is an effective treatment method and that patients with retained products of pregnancy <50mm in diameter and stable vital signs are suitable for expectant management. However, there is a difference in the effectiveness of expectant management compared to surgical management. Patients who undergo curettage can completely expel the remaining pregnancy tissues through surgery in a short period of time, so curettage is considered to be a more effective treatment method. In fact, clinicians are usually worried that the continued presence of pregnancy tissues in the uterus may lead to serious complications such as bleeding or infection. Therefore, they tend to actively treat the disease to reduce the incidence of complications. However, some studies have shown that there is no statistically significant difference in the risk of patients needing emergency curettage for massive bleeding, whether they undergo expectant management or curettage. On the contrary, curettage may increase the risk of postoperative infection ^[8]. With repeated intrauterine operations, the incidence of intrauterine adhesions gradually increases. Intrauterine adhesions seriously affect menstrual recovery and subsequent pregnancy, and have become an important cause of infertility. Some studies have reported that the incidence of intrauterine adhesions after curettage is about 29.6%, and the incidence of intrauterine adhesions in patients who undergo curettage again after incomplete abortion due to pregnancy tissue residue can increase to 40%, of which 75% are moderate to severe intrauterine adhesions ^[9]. 83.1% of patients with severe intrauterine adhesions had related curettage for pregnancy ^[10]. In fact, the incidence of intrauterine adhesions may be more than that. Since the typical clinical manifestation of intrauterine adhesions is reduced menstrual flow, and severe cases are accompanied by secondary infertility, it mainly affects the patient's fertility, but has no significant impact on daily life. Therefore, some patients do not seek medical attention or receive related treatment. Therefore, for patients who want to have children, expectant management is a good choice to reduce the number of intrauterine procedures, prevent the occurrence of intrauterine adhesions, and protect the patient's fertility.

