4.1.2 Expectant Treatment Group

1) In the outpatient clinic, complete routine examinations of vaginal secretions, blood β -HCG, complete blood count, CRP, procalcitonin (optional), chlamydia and gonococcus, and other infection indicators. If the 4D color ultrasound indicates placenta accreta or retained products of conception in special locations such as the uterine horn or cesarean section incision site (CSP), and if necessary (especially when CSP or interstitial retained products of conception cannot be ruled out), complete a pelvic MRI plain scan with contrast. At the same time, complete liver and kidney function tests and coagulation function tests.

2) For patients without contraindications, administer 2mg of Progynova twice daily (or a similar dose of Estradiol) until postoperatively (generally, continue using Progynova for 2-4 weeks postoperatively with progesterone withdrawal bleeding); then

discontinue oral administration of Leonurus japonicus granules or Acanthopanax senticosus capsules for 2 weeks.

4D color Doppler ultrasound of the uterus and adnexa every 2-3 weeks ; until **the predetermined surgical timing is reached** : 1) Blood β -HCG <50mmol / L; 2) Ultrasound measurement of the length from the internal cervical os to the fundus \leq 6cm; 3) At least 4 weeks between the previous surgery; 4) Color Doppler ultrasound showing blood flow grade 1-3 at the pregnancy tissue and attachment site . This predetermined surgical timing is proposed based on our hospital's summary of previous patient data and literature analysis. Research hospitals can adjust the surgical timing parameters according to clinical experience. Patients who reach the predetermined surgical timing will be hospitalized, undergo relevant examinations, and undergo hysteroscopic removal of the pregnancy tissue (hysteroscopic surgery using a large cold knife instrument is recommended ; refer to the surgical video).

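### Sections 5.1 and 5.2 do not list how the index pregnancy ended and do not separate evacuations already done for it from earlier procedures, so an important potential confounder of the adhesion comparison can be only partly controlled.

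*Protocol*

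**What the plan says.** Section 5.1 (General information) sets the history items as "age, parity, number of previous intrauterine procedures, history of intrauterine adhesions, occupation, and education level". The procedure item is a bare count, without date, type or link to a particular pregnancy.

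Section 5.2 opens with the index-pregnancy items, "gestational age at termination; time of termination", and goes on to serum β-HCG and imaging, including adhesions seen at baseline. Neither section 4.3 nor section 5 lists whether the pregnancy ended in delivery, miscarriage, or medical or surgical termination. Neither lists as a separate item whether the uterus had already been evacuated for it.

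The background ties such procedures to the primary outcome. It reports that "the incidence of intrauterine adhesions after curettage is about 29.6" (per cent), that the figure for women "who undergo curettage again after incomplete abortion due to pregnancy tissue residue can increase to 40" (per cent), and that "83.1% of patients with severe intrauterine adhesions had related curettage for pregnancy".

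The clinic already takes part of this history: the background bases diagnosis partly on "the patient's history of delivery or miscarriage". Groups follow the patient's wishes with physician guidance (section IV.2). The main indicator is the incidence of adhesions (6.1), and section 8 names a χ² or Fisher test for count data.

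**The concern.** In a comparison formed by choice, a factor that affects both the choice and the outcome biases the crude difference. A recent evacuation for the same pregnancy is a plausible factor of this kind. It may influence whether a woman accepts another operation or prefers to wait, and by the protocol's own figures it bears on adhesion risk.

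Such women can be enrolled. No exclusion criterion removes them, and the note to the eligibility criteria admits women who have already had tissue clamped from the cervical canal.

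As listed, a woman with one curettage five years ago and a woman with one curettage five weeks ago receive the same value. The study hypothesis is that fewer intrauterine procedures mean fewer adhesions, so this blurs the history most relevant to it. A statistical analysis plan can choose covariates, but it cannot adjust for a distinction that was never recorded.

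**Working it through.** **Data-list check.**

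| Information | Listed? |
|---|---|
| How the index pregnancy ended | No |
| Evacuation already done for it (number, type, date) | Not separately; possibly inside the 5.1 count |
| Earlier procedures, all pregnancies | Count only (5.1) |
| Adhesion history; adhesions on baseline imaging | Yes (5.1; 5.2) |
| Gestational age and time of termination | Yes (5.2) |

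**Planned difference (section IV.3).** The rates are 14.29% and 5.38%, so the difference is 8.91 points and the design average is (14.29 + 5.38)/2 = 9.835%. The stated sample size reproduces with unpooled variance, two-sided α 0.05, 90% power and 1:1 allocation (sidedness and ratio are not stated and are assumed here):

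n = (1.960 + 1.282)² × (0.1429×0.8571 + 0.0538×0.9462) / 0.0891², rounded up to 230 per group, or 460 in total. With 20% dropout, 230/0.8 = 287.5, rounded up to 288 per group, or 576. The point below does not alter these numbers.

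**Size of bias, assuming no treatment effect.** Let a and b be the shares already evacuated in the two groups, m = (a + b)/2, and RR the risk ratio for prior evacuation. With overall risk fixed at 9.835%:

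- risk in the non-evacuated: r0 = 9.835 / (1 + (RR − 1)m)
- spurious difference: r0 × (RR − 1) × (a − b)

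The documents give neither the shares nor RR, so both are assumed. The lowest RR is the protocol's 40/29.6 = 1.35. Each cell shows the spurious difference in points, its share of 8.91, and the rejection rate of the unadjusted test (pooled normal approximation, 230 per group, nominal 5%).

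| RR | 60% v 50% | 60% v 40% | 70% v 40% |
|---|---|---|---|
| 1.35 | 0.29; 3%; 5.1% | 0.59; 7%; 5.5% | 0.87; 10%; 6.1% |
| 2 | 0.63; 7%; 5.6% | 1.31; 15%; 7.6% | 1.90; 21%; 10.5% |
| 3 | 0.94; 11%; 6.3% | 1.97; 22%; 10.9% | 2.81; 32%; 17.3% |
| 4 | 1.11; 12%; 6.9% | 2.36; 26%; 13.6% | 3.34; 37%; 22.5% |

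Top corner: r0 = 9.835/(1 + 3×0.55) = 3.71%, and the bias is 3.71 × 3 × 0.30 = 3.34 points.

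The table illustrates the size and does not bound it. The average share m stands in the denominator, so the same imbalance around a smaller average share gives a larger bias.

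**Cross-check on the protocol's absolute rates.** The contrast is 40 − 29.6 = 10.4 points. A 10-point imbalance gives 0.10 × 10.4 = 1.0 point and a 30-point imbalance gives 3.1. Producing the whole planned difference would need an imbalance of 8.91/10.4 = 86 points.

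**The case against.** The strongest reply is that the information is not certainly missing. On a plain reading, a curettage done weeks before enrolment is an earlier intrauterine procedure and enters the 5.1 count. Adhesion history, adhesions on baseline imaging, gestational age and time of termination are also collected, and section 4.2.2 has pre-existing adhesions described at operation. The case report form is a separate document that is not shown and may hold more. This stands, and it limits the point to incomplete control. It does not remove it, because the count cannot tell an index-pregnancy evacuation from an older one and the text does not say whether it includes the former.

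Four stronger readings are tempting, and the documents do not support them.

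- *This is the main confounder.* No figure links prior evacuation to treatment choice. Lesion size, β-HCG, uterine length and blood flow may also drive choice, and all are collected.
- *The bias cannot be removed at all.* The proxies above may remove part of it, and the history can probably be retrieved from records.
- *The timing rule steers recently operated women towards waiting.* The criterion "At least 4 weeks between the previous surgery" sits in 4.1.2 and governs when women already in the expectant group are operated on. It does not allocate treatment. Because 4.2.3 returns women with residue above 0.5 cm to expectant management, the surgery meant may be the study operation.
- *The bias could reach most of the planned effect.* Setting 29.6% against 5.38% with a 30-point imbalance gives 0.30 × 24.22 = 7.3 points, or 82% of 8.91. But 5.38% is the rate for the whole expectant group, and the protocol gives no rate for never-evacuated women. With an average of 9.835%, those two rates imply (9.835 − 5.38)/24.22 = 18% evacuated overall, so a 30-point gap would mean about 33% against 3%, an extreme split.

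It is also fair to say that new fields alone change nothing if only the unadjusted test is run. Adjustment may be set out in an analysis plan not shown here, but that plan would still need the data.

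**Conclusion.** The point holds in a limited form. The listed data omit how the index pregnancy ended and do not separate evacuations for that pregnancy from earlier procedures. Treatment is chosen, and the protocol itself links curettage and repeat curettage to the primary outcome, so this is an important potential confounder that the listed items can control only in part.

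Under the assumptions shown (overall risk 9.8%, risk ratios 1.35 to 4, imbalances of 10 to 30 points around average shares of 50 to 55%), the spurious difference is about 0.3 to 3.3 points, or 3 to 37% of the planned 8.91. The unadjusted test would then reject in about 5 to 22% of studies with no treatment effect. The low end is negligible and the upper part is not. The direction cannot be known in advance, because the documents do not show which group would contain more women already evacuated. The change is worth making because it is cheap and because information not recorded at enrolment is harder to obtain later.

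**What to change.** 1. Add to section 5.2, for every woman at enrolment and from history or records: how the index pregnancy ended, and the number, type and date of any uterine evacuation already done for it.
2. State in section 5.1 whether the procedure count includes those evacuations.
3. Report both new items by treatment group, and adjust or stratify the adhesion comparison for them, alongside the unadjusted test.

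Cost: a few extra case-report-form fields and some retrospective record review for women already enrolled, where older records may be incomplete. No added examination or visit is needed, which fits the protocol's commitment to routine care, and the sample size of 460 (576 with dropout) is unchanged.
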